6.0 Study Design

This is a Phase 1 randomized, double-blind, placebo-controlled, 4-way crossover study of LY3526318 in healthy female participants.

All participants will have 2 screening visits with the first to evaluate the health of the participant and the second visit to undergo an LDI assessment to ensure a response of at least 100% increase in DBF between pre- and post-CA challenge. Following a screening period of up to 28 days, eligible participants will be confined to the clinical research unit from Day 1 until all assessments are completed on Day 2 of each dosing period.

As summarized in [Table 1](#), each participant will be randomly assigned to 1 of 4 treatment sequences, with a ratio of 3 LY3526318: 1 placebo. Each participant will receive 3 doses of LY3526318 and 1 dose of placebo in a crossover manner, with at least 6 days of washout between doses. The planned dose levels of LY3526318 are anticipated not to exceed the maximum administered dose in the SAD portion of Study CVAA.

Table 1 Treatment Sequence

Sequence	N	Period 1	Period 2	Period 3	Period 4
P132	4	P	D1	D3	D2
12P3	4	D1	D2	P	D3
231P	4	D2	D3	D1	P
3P21	4	D3	P	D2	D1

During each visit (screening and study periods), each patient will undergo at least 30 minutes acclimatization and placement of 3 rubber O-rings on the volar surface of the forearm. Prior to study drug administration, a pre-drug DBF will be collected without CA. For each time point following study drug administration, pre-CA measurements will be performed for the areas defined by the rings within 10 minutes before CA application. After the pre-CA measurements, a 20 μ L topical dose of 10% CA will be applied in the proximal O-ring of the participant's forearm. Using the same procedure, a 20 μ L topical dose of 3% CA will be applied in the medial ring, followed by a 20 μ L topical dose of the vehicle solution to the distal ring. LDI/LSCI measurements will again be performed approximately 20 minutes after CA and vehicle applications. Specific details of the procedure will be agreed upon and documented between the sponsor and investigator and research staff operating the equipment.

All assessments will be performed as defined in Schedule of Activities ([Appendix 2: Schedule of Assessments](#)).

All participants will attend a safety follow-up visit about 7 days following the last dose of study drug.

6.1 Sample Size Considerations

The sample size is justified based on the statistical power to meet the primary endpoint of DBF measurements from LDI assay at t_{max} . The power calculation used 10% CA-induced absolute DBF in comparison between LY3526318 and placebo arms. For a 20% reduction in DBF (assuming mean observed placebo DBF of 444.3 arbitrary perfusion units (PU) with standard deviation (SD) of 55.1 PU) and a significance level of 0.05, a paired t-test with 16 patients results in 98% power to reject the null hypothesis. Incorporating a Bonferroni adjustment to account for multiplicity (changing the significance level to 0.05/3) lowers the power slightly to 96%.

6.2 Randomization

A randomization schedule will be prepared by the Biostatistics Department of PRA. Subjects (numbered 01-16) will be assigned to one of the 4 sequences. The subjects are to be assigned to a treatment sequence in blocks of 4 (with subject numbers 01-04, 05-08, 09-12 and 13-16), with each of the 4 sequences assigned once in each of the 4 blocks.

7.0 Overview of Planned Analysis

7.1 Changes from Protocol

There are no changes from the protocol.

7.2 Interim Analysis and Key Results

There will be no interim analyses or summaries of data provided prior to the delivery of the full set of post-lock tables, figures and listings (TFLs).

7.3 Final Analysis

Draft TFLs will be provided with the draft CSR. After Sponsor comments have been incorporated, the TFLs will be finalized and incorporated in the final CSR.

8.0 Data Review

8.1 Data Management

Data handling and transfer will take place under the PRA Data Management Plan for the study.

8.2 Acceptance of Data for Summarization

Programming of analysis datasets and TFLs may be ongoing during the data management of the study. However, programming of analysis datasets and TFLs will be completed and quality controlled (QC'd) after database lock. Only quality assured (QA'd) results released by the Safety Laboratory, Bioanalytical Laboratory, or other external data source will be used for the programming of analysis datasets and TFLs for the final report. Any data values requiring investigation or corrections that are identified while programming the analysis datasets and TFLs will be sent to the project Data Manager. If the issue affects the TFLs the Programmer or Statistician who identified the issue will follow it to resolution.

9.0 Definitions and General Analysis Methods

9.1 Analysis Data Presentation

9.1.1 Rounding

In listings, data will be presented with the same precision as the original data. Derived data will be rounded for presentation purposes.

For all summaries, all descriptive statistics will be presented to the same number of decimal places as the original data.

Frequency percentages will be presented with one decimal.

Percentage change for PD measurements will be presented with one decimal.

Derived parameters will generally be presented with three significant figures.

P-values will be reported to four decimal places; p-value less than 0.0001 will be reported as “<0.0001”.

9.1.2 Imputation

Unless otherwise noted, data will not be imputed.

Missing start or end times for AEs will be imputed as described in [18.1.1](#).

PK concentrations below the quantifiable limit (BQL) will be replaced as described in [16.2](#).

9.1.3 Descriptive Statistics

Unless otherwise indicated, continuous variables will be summarized with the following descriptive statistics: n (number of observations), (arithmetic) mean, SD, minimum (min) value, median, and maximum (max) value.

Categorical data will be summarized with frequencies and percentages. Percentages by categories will be based on the number of subjects exposed within a treatment.

For categorical data the categories will be presented in the tables exactly as they appear in the eCRF / Database. When there is a difference between the descriptions of categories in the eCRF and the database, the description in the database will be used.

9.1.4 Pooling

Summary statistics will be calculated by treatment (and time point, if applicable).

9.1.5 Unscheduled Measurements

Unscheduled measurements will be included in the listings. With the exception of unscheduled measurements used for baseline, unscheduled measurements will be excluded from the descriptive statistics and statistical analysis.

9.2 Analysis Data Definitions

9.2.1 Baseline Definition

Unless otherwise stated, baseline for post-dose evaluations within each period is defined as the last observation recorded before the study drug administration in each period. The last observation can be an unscheduled / repeated measurement.

9.2.2 Treatment/Subject Grouping

Label	Grouping
Treatment	Placebo LY3526318 x mg LY3526318 y mg LY3526318 z mg
Treatment abbreviated	P D1 D2 D3
Treatment numeric	0 1 2 3

9.2.3 Common Variable Derivations

Variable	Data Type	Definition/Calculation	Note
Change from Baseline	All	Post-dose Observation minus Baseline Observation	Within period
Analysis Study Day (Prior to Dose)	All	Date of Measurement minus Dose Date	Within period
Analysis Study Day (Post Dose)	All	Date of Measurement minus Dose Date +1	Within period

9.2.4 QC

The analysis datasets and the TFLs will be QC'd according to the general PRA EDS QC plan.

9.2.4.1 Critical Data

The QC plan requires datasets be classified as critical or non-critical. As the end point related to the primary objective of this study is CA-induced DBF, the dataset considered critical are pharmacodynamic data (ADPD). Therefore this dataset will be double programmed per the QC Plan.

9.2.5 ADaM Datasets and Metadata

Analysis datasets that will be created are subject level (ADSL), AE (ADAE), clinical laboratory (ADLB), electrocardiogram (AEG), vital signs (ADVS), pharmacokinetic concentrations (ADPC) and pharmacodynamic DBF results (ADPD).

The analysis datasets will be generated in accordance with Clinical Data Interchange Standard Consortium (CDISC) Analysis Data Model (ADaM) Version 2.1.

A define.xml file version 2 will be created. Analysis results metadata are excluded.

9.3 Software

The statistical analysis and reporting will be done using SAS® for Windows™ Version 9.4 or higher (SAS Institute, Inc.).

9.4 Statistical Methods

9.4.1 Statistical Outlier Determination

No statistical outlier analysis is planned.

9.4.2 Predetermined Covariates and Prognostic Factors

There are no predetermined covariates or prognostic factors.

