During each visit (screening and study periods), each patient will undergo at least 30 minutes acclimatization and placement of 3 rubber O-rings on the volar surface of the forearm. Prior to study drug administration, a pre-drug DBF will be collected without CA. For each time point following study drug administration, pre-CA measurements will be performed for the areas defined by the rings within 10 minutes before CA application. After the pre-CA measurements, a 20 μ L topical dose of 10% CA will be applied in the proximal O-ring of the participant's forearm. Using the same procedure, a 20 μ L topical dose of 3% CA will be applied in the medial ring, followed by a 20 μ L topical dose of the vehicle solution to the distal ring. LDI/LSCI measurements will again be performed approximately 20 minutes after CA and vehicle applications. Specific details of the procedure will be agreed upon and documented between the sponsor and investigator and research staff operating the equipment.

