10.3.3. Pharmacodynamic Analyses

The primary endpoint is the percent change from pre-CA to CA-induced DBF as measured by LDI, compared to placebo at 3 hours post-dose. Summary statistics for each cohort will be provided by treatment. Mixed-effect model for repeated measure (MMRM) will be used to evaluate the primary endpoint including covariates such as treatment, period, carry-over, and sequence. Similar analyses will also be conducted for LDI at 24 hours post dose as well as DBF outcomes as measured by LSCI (laser speckle contrast imaging) at 3 hours and 24 hours.

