17.0 Pharmacodynamic Analysis

17.1 Pharmacodynamic Variables

PD assessments will be DBF measured by two methods, LDI and LSCI. For time points with a pre- and post-CA measurement available, the percentage change will be calculated.

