17.2.2 Statistical Analysis

An analysis of variance (ANOVA) will be performed on the percentage change (pre- to post-CA) at time points 3 h and 24 h post-dose using PROC MIXED in SAS. The percentage change will be used untransformed in the analysis. The model will include fixed effects for treatment, period, sequence, time and treatment*time interaction and a random effect for subject within sequence. The analysis will be done for each, method and CA concentration separately. From this model the least-squares means (LSMeans) for each treatment (including placebo) and the difference of the LSMeans for each of the active treatments with placebo at 3 h and at 24 h post-dose and the corresponding P value will be estimated for each method and CA concentration.

In the summary of the statistical analysis, it will be indicated that the result for LDI, 3 hours post-dose is the primary end point.

In SAS code:

```

proc mixed data=dbf;
  by CAconc method;
  class subject trtan time           period seq;
  model pchg = trtan time trtan*time period seq;
  random subject(seq);
  lsmeans trtan*time ;
  /*estimates*/
run;
quit;

```

For each of the active dose levels and CA concentrations, a decrease relative to placebo of the percentage change (pre- to post-CA) with a P value below (0.05/3) will be considered statistically significant.

Additionally, the same model (with fixed effects for treatment, period, sequence, time and treatment*time interaction and a random effect for subject within sequence) will be applied to the absolute values for each method and CA concentration separately, using data from all time points (i.e. pre study drug, 3 h pre- and post-CA, 24 h pre- and post-CA). From this model, using the absolute values, LSMeans and the differences with 90% CI and P-value will be estimated for each method and CA concentration for the following comparisons:

#	LSMean (absolute value) of	Compared with LSMean (absolute value) of
1	D1 post-CA at 3 h	Placebo post-CA at 3 h
2	D2 post-CA at 3 h	Placebo post-CA at 3 h
3	D3 post-CA at 3 h	Placebo post-CA at 3 h
4	D1 post-CA at 24 h	Placebo post-CA at 24 h
5	D2 post-CA at 24 h	Placebo post-CA at 24 h
6	D3 post-CA at 24 h	Placebo post-CA at 24 h
7	Placebo pre-CA at 3 h	Placebo pre study drug at 0 h
8	D1 pre-CA at 3 h	D1 pre study drug at 0 h
9	D2 pre-CA at 3 h	D2 pre study drug at 0 h
10	D3 pre-CA at 3 h	D3 pre study drug at 0 h
11	Placebo pre-CA at 24 h	Placebo pre study drug at 0 h

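### The primary percentage-change model leaves unused the pre-drug resting flow collected in every period: a cheap, conditional gain in precision, not an error

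*SAP*

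**What the plan says.** Protocol 9.6.1 provides for a resting scan in each period: "Prior to study drug administration, a pre-drug DBF will be collected without CA". The Schedule of Activities lists it for both laser Doppler (LDI) and laser speckle imaging in all four periods.

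The primary response does not use that scan. Protocol 10.3.3 defines it thus: "The primary endpoint is the percent change from pre-CA to CA-induced DBF as measured by LDI, compared to placebo at 3 hours post-dose". SAP 17.1 agrees: "For time points with a pre- and post-CA measurement available, the percentage change will be calculated". The reference value is therefore the pre-CA scan at the same post-dose time point, although the general rule in SAP 9.2.1 is that "baseline for post-dose evaluations within each period is defined as the last observation recorded before the study drug administration in each period".

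For the primary model, SAP 17.2.2 says "The model will include fixed effects for treatment, period, sequence, time and treatment*time interaction and a random effect for subject within sequence", and SAP 9.4.2 adds "There are no predetermined covariates or prognostic factors". The pre-drug scan enters only descriptive summaries and the additional absolute-value model, where it is a response level ("using data from all time points (i.e. pre study drug, 3 h pre- and post-CA, 24 h pre- and post-CA"; comparisons 7 to 14).

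The protocol's own model description lists terms "including covariates such as treatment, period, carry-over, and sequence". It does not mention a baseline DBF.

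**The concern.** Percentage change divides post-CA flow by resting flow and is analysed untransformed. Day-to-day variation in resting flow therefore enters the response through its denominator. The crossover removes stable differences between participants, but not this within-participant variation.

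The 3 h pre-CA scan follows dosing, and the SAP itself tests whether resting flow has moved by then (comparisons 8 to 10). The 0 h scan is the only resting measurement in a period that the period's dose cannot have affected. If it predicts the 3 h resting flow, using it would narrow the three primary contrasts without new data. With 16 participants and a threshold of 0.05/3, that is worth considering.

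**Working it through.** **Inputs from the documents.** n = 16, placebo mean 444.3 PU, SD 55.1 PU, 20% reduction, alpha 0.05/3 (SAP 6.1); four sequences over four periods (Protocol Table 5-1).

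**Assumed, because the documents give none of them.** Resting mean 60 or 120 PU; within-participant CV of resting flow 15% or 30%; same-day correlation ρ of resting flow between 0 h and 3 h; exponent k by which post-CA flow scales with same-day resting flow (k = 0 independent, k = 1 fully proportional).

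**1. The plan's own figure.** The difference is 0.20 × 444.3 = 88.86 PU. Read 55.1 PU as the per-treatment SD with zero within-participant correlation: the SD of a difference is 55.1 × √2 = 77.9 PU. A two-sided paired t-test on 15 df then has power 98.9% at 0.05 and 95.7% at 0.05/3, against the stated 98% and 96%. The figures reproduce, but they are for absolute post-CA flow. They do not measure precision on the percentage-change scale.

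**2. Cost of one covariate.** At one time point there are 64 observations. Participants (16), periods (3) and treatments (3) use 22 parameters, leaving 42 residual df, or 41 with a covariate. The expected inflation of the contrast variance is 1 + 1/40 = 1.025.

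**3. Gain for a given correlation.** If r is the within-participant correlation of covariate and response, adjusted/unadjusted variance ≈ 1.025 × (1 − r²): 1.025 at r = 0, 0.984 at 0.2, 0.769 at 0.5. Simulation on the crossover gave 1.025, 0.984 and 0.78. The adjusted analysis had the larger estimated variance in 78%, 50% and 3% of simulated trials.

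**4. What r could be here.** The response is 100 × (P/R − 1), with P post-CA and R resting flow. If P varies as R to the power k, plus independent noise with relative SD c = 55.1/444.3 = 0.124 (c² = 0.0154), then to first order

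r² = ρ² × (1 − k)²CV² / [(1 − k)²CV² + c²].

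For k = 0 and CV 15%, the fraction is 0.0225/(0.0225 + 0.0154) = 0.594. For CV 30% it is 0.0900/(0.0900 + 0.0154) = 0.854. At ρ = 0.5 the variance ratios are 1.025 × (1 − 0.25 × 0.594) = 0.87 and 1.025 × (1 − 0.25 × 0.854) = 0.81. At k = 1 the fraction is zero and only the 1.025 penalty remains. The resting mean cancels.

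**5. Simulation of the Table 5-1 design** (percentage change at one time point; participant, period and treatment, with and without log pre-drug DBF), adjusted/unadjusted contrast variance:

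| Post-CA flow | ρ = 0 | ρ = 0.2 | ρ = 0.5 | ρ = 0.8 |
|---|---|---|---|---|
| Independent of resting flow (k = 0) | 1.02–1.03 | 0.99–1.01 | 0.83–0.89 | 0.54–0.69 |
| Half scaling (k = 0.5) | – | – | 0.89–0.97 | 0.66–0.86 |
| Full scaling (k = 1) | 1.02–1.03 | 1.02–1.03 | 1.02–1.03 | 1.02–1.03 |

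The simulated gain is somewhat smaller than step 4 suggests. One reason is that a fixed 55.1 PU is relatively larger at the reduced flow: 55.1/(0.8 × 444.3) = 0.155. With independent post-CA flow, mean contrast estimates moved by at most 1.2 percentage points, in no consistent direction. The ranges shift by a few points with the details of data generation.

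**Limit of the check.** Steps 2 to 5 use one time point with participant as a fixed effect. The SAP model fits 3 h and 24 h jointly with a random participant effect, and the ratios were not computed for that model.

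**The case against.** The best defence is that baseline is already handled. The pre-CA scan is taken within ten minutes of CA application, in the same rings, which is a closer reference than a scan about three hours older. If post-CA flow is proportional to resting flow, the ratio cancels the shared variation and the covariate only costs precision. That stands, and the last row of the table shows it. It fails only if scaling is incomplete; noise in the denominator then remains in the response.

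Other objections also stand:
- The pre-drug scan measures resting flow, not a CA response.
- Protocol 9.6.1 puts the 3 h and 24 h challenges on opposite forearms and does not say which forearm the pre-drug scan uses, so one scan may match only one time point.
- In Periods 2 to 4 the scan follows earlier doses and challenges. It is protected from the current period's dose, not from any carry-over.

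A reader might infer that SAP 9.4.2 bars all adjustment or drops something the protocol promised. The documents do not support this: period and sequence are in the model, each participant is her own control, and the protocol's list contains no baseline DBF. The list's carry-over term, absent from the SAP model, is a separate matter. A reader might also infer that the gain is certain and free. That does not follow either, since both conditions for a gain are unreported and the covariate uses degrees of freedom.

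**Conclusion.** The point holds as a missed, inexpensive improvement to a defensible model. The possible outcomes are lopsided: at worst about 3% more contrast variance, when the scan is uninformative or scaling is full; about break-even at a same-day correlation of 0.2; 11 to 17% less at 0.5 and 31 to 46% less at 0.8 if post-CA flow is independent of resting flow; intermediate gains under partial scaling. These sizes rest on the assumed resting means, CVs, correlations and scaling. Some same-day correlation is plausible, because the scans are about three hours apart under the same resting conditions, but the documents do not show it. Nothing here suggests that the planned unadjusted analysis is biased or invalid.

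**What to change.** Before unblinding, amend SAP 9.4.2 and 17.2.2 for the percentage-change model:

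- Name log pre-drug DBF, from the same method and ring, as a covariate. Enter it as the participant's mean and the period's deviation from that mean, so that between- and within-participant slopes are not mixed.
- Let the slope differ by time point, because 3 h and 24 h use opposite forearms.
- State which forearm the pre-drug scan uses, and the rule for a period in which it is missing.
- Keep the unadjusted model as a sensitivity analysis.

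No new data are needed. The absolute-value model, fitted by CA concentration, already calls for pre-drug values in the analysis dataset. The cost is a few model terms, one to a few degrees of freedom, and up to about 3% more contrast variance if the covariate proves uninformative. Once treatments are unblinded, the same change could no longer be presented as prespecified.

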9.4.3 Hypothesis Testing

Significance testing will be 1-sided at the significance level of 0.05/3 for the primary statistical analysis.

9.5 TFL Layout

Report layout will be according to the PRA EDS – ICH E3 compliant – CSR Template. The layout of TFLs will be according to the PRA EDS standards.

No table shells will be provided. The TFLs will be provided in Adobe PDF format.

Format:

- Page size: A4
- Data in listings will be sorted by subject number and time point.
- Data in tables will be sorted by treatment and time point.
- Column titles will be in title case letters.
- All tables and listings will be in landscape format.
- The treatment labels will be as outlined in [9.2.2](#).

10.0 Analysis Sets

Analyses	Randomized Set	Safety Set	Pharmacodynamic Set
Disposition Summaries	✓		
Safety Assessments		✓	
Baseline Characteristics		✓	
Primary Analysis			✓
PK Concentrations		✓	
PD Parameters			✓

10.1 Randomized Analysis Set

The all subjects randomized analysis set (RAND) will consist of subjects who are assigned a randomization number in the study. This set will be used for disposition summaries.

10.2 Safety Analysis Set

The safety analysis set (SAF) will consist of subjects who receive at least one dose of LY3526318 or placebo. This set will be used for the safety data summaries, baseline characteristic summaries, and PK concentration summaries.

10.3 Pharmacodynamic Analysis Set

The pharmacodynamic analysis set (PDAS) will consist of all subjects who receive LY3526318 or placebo at least once and have at least one reliable post-dose PD measurement (LDI or LSCI).

Available data from drop-outs will be included in summaries.

Data from drop-outs will be included in statistical analysis if data are available for at least the placebo and one active treatment.

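### SAP 10.3 keeps drop-outs without placebo data out of a mixed model that could use them: a small, avoidable loss of precision

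*SAP*

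**What the plan says.** SAP 10.3 admits to the pharmacodynamic analysis set (PDAS) any dosed subject with one usable post-dose reading by either imaging method. Placebo data are not required. Two sentences then treat drop-outs differently by type of output. For description: "Available data from drop-outs will be included in summaries". For inference: "Data from drop-outs will be included in statistical analysis if data are available for at least the placebo and one active treatment".

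SAP 17.2.2 defines the model: "The model will include fixed effects for treatment, period, sequence, time and treatment*time interaction and a random effect for subject within sequence".

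SAP 6.0, Table 1 (the same design as Protocol 5.1, Table 5-1) gives four sequences of four participants, with placebo in a different period in each: "P132 4 P D1 D3 D2", "3P21 4 D3 P D2 D1", "12P3 4 D1 D2 P D3" and "231P 4 D2 D3 D1 P".

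PD data are not imputed (SAP 9.1.2). Withdrawn participants may be replaced, but only at the sponsor's discretion (Protocol 8).

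**The concern.** A mixed model with a random subject effect does not need each participant to supply both placebo and active data. A participant with active periods only still informs the period effects and the dose-to-dose differences. Through these and the random subject effect, that participant also adds something to the dose-placebo contrasts. Removing such a participant discards primary-endpoint data already collected in a 16-person trial.

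Because placebo moves across periods, two participants who leave after the same number of periods can be treated differently purely because of their randomised sequence. A 231P drop-out can never enter the model, even after completing all three active periods.

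The descriptive and model tables of LDI results (SAP Appendix 3, Tables 12.4.2.2 and 12.4.2.4) are both labelled PDAS, yet could rest on different participants.

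**Working it through.** **The plan's own figure.** SAP 6.1 gives a placebo mean of 444.3 PU, SD 55.1 PU, a 20% reduction, n = 16, and power of 98% (0.05) and 96% (0.05/3).
- Effect: 0.20 × 444.3 = 88.86 PU.
- SD of the paired difference at an assumed within-subject correlation of 0: 55.1 × √2 = 77.9.
- Noncentrality: 88.86 / (77.9/√16) = 4.56.
- Two-sided power: 98.9% at 0.05 and 95.7% at 0.05/3, within a point of the stated values.

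This calculation assumes 16 complete pairs and does not involve the drop-out rule.

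**Step 1: apply the rule to each sequence.** Treatments completed, and whether the drop-out enters the model:

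| Sequence | After 1 period | After 2 periods | After 3 periods |
|---|---|---|---|
| P132 | P: out | P, D1: in | P, D1, D3: in |
| 3P21 | D3: out | D3, P: in | D3, P, D2: in |
| 12P3 | D1: out | D1, D2: out | D1, D2, P: in |
| 231P | D2: out | D2, D3: out | D2, D3, D1: out |

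The sequences differ only for departure after two or three completed periods.

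**Step 2: cost in precision.** Assumptions: four participants per sequence; fixed treatment, period and sequence effects; random subject effect; one value per period (a simplification, since the SAP model holds 3 h and 24 h jointly); known variance components. The documents give no intra-subject correlation ρ, so ρ runs from 0 to 0.7.

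In units of within-subject variance, V = I + [ρ/(1−ρ)]J for each participant. The information matrix is M = Σ X′V⁻¹X, and the variance of each dose-minus-placebo contrast is read from M⁻¹. With no drop-outs this is 2/16 = 0.125.

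SAP rule against all available data:

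| Drop-outs | ρ | Rule | All data | Increase under rule |
|---|---|---|---|---|
| One 231P after period 3 | 0 | 0.1339 | 0.1296 | 3.3% |
| | 0.5 | 0.1339 | 0.1306 | 2.5% |
| | 0.7 | 0.1339 | 0.1308 | 2.4% |
| Two 231P after period 3 | 0 | 0.1458 | 0.1364 | 6.9% |
| | 0.5 | 0.1458 | 0.1383 | 5.4% |
| | 0.7 | 0.1458 | 0.1386 | 5.2% |

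One 12P3 drop-out after period 2, at ρ = 0.5, gives 0.1339 against 0.1310 for D1 and D2 (2.2%) and no change for D3.

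Two 231P drop-outs after period 3 plus one 12P3 drop-out after period 2 leave 13 participants in the model. The increase is then 6.0 to 11.7% by dose and correlation: 7.8 to 11.7% at ρ = 0 and 6.0 to 7.8% at ρ = 0.7. (Percentages are from unrounded variances.)

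**Step 3: a typical case.** Averaging over the 12 cells of the Step 1 table with equal weight, and over the three doses, one drop-out raises the variance by about 1.2% at ρ = 0 and 0.6% at ρ = 0.7.

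**Step 4: bias.** A small simulation at ρ = 0.5, with about 3 of 16 participants leaving either at random or depending on response, gave bias of at most 0.012 within-subject SD under either rule.

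**The case against.** The rule is explicit and prespecified. It limits inference to participants who can supply a within-person dose-placebo comparison, which is the trial's stated contrast; anyone without placebo adds only indirect information. The larger percentages need one or two of the four 231P participants to leave exactly after period 3, and no drop-out rate is given. Two drop-outs at random cost 1.2 to 1.8% for ρ from 0.7 to 0.3.

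On the planning values, with ρ = 0 and the SAP's one-sided 0.05/3, power with one 231P drop-out is 98.4% under the rule and 98.7% without it. In the three-drop-out case the lowest power over the doses is 96.4% against 97.6%. SAP 11.0 reports disposition by sequence, so a reader could see who was affected, and replacement may restore a lost slot.

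All of this stands as to size. It does not give the rule any benefit in this model; at best it supports the restricted subset as a secondary look.

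Four stronger readings are tempting and are not supported:
- *Selection bias.* Sequence is randomised, the model adjusts for period and sequence, and the simulation shows no material bias.
- *Placebo-late sequences always lose and the others always keep their drop-outs.* After one period all four sequences are excluded, and a 12P3 drop-out after period 3 is kept.
- *The data vanish from the report.* They leave the model only; listings and summaries keep them.
- *The rule is a leftover from the paired t-test used for sample size.* The documents state no reason for it.

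**Conclusion.** The point holds as a modest, avoidable inefficiency. The condition is unnecessary for the specified model and makes retention after two or three completed periods depend on sequence. Its price is a dose-placebo variance about 2.4 to 3.3% larger for one 231P drop-out after period 3, 5 to 7% for two, and 6 to 12% by dose in the three-drop-out case. It is around 1% for one drop-out at a random sequence and time, and zero if no affected participant leaves.

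These figures rest on the assumed correlation range, one value per period and known variance components. They do not show bias or undermine the power statement, and on the planning values the change in power is about a percentage point at most in the cases compared. The improvement is worth making because it is free, but it is optional in priority.

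**What to change.** In SAP 10.3, delete the sentence that makes entry to the statistical analysis conditional on placebo plus one active treatment. State in its place that all available post-dose PD records of every PDAS participant enter the PROC MIXED model, whether or not placebo data exist. If the sponsor values the restricted comparison, keep the placebo-plus-one-active subset as a sensitivity analysis.

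The cost is one sentence in the SAP, with no new data and no change to the model code. The sensitivity analysis, if wanted, is one more run of the same model.
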